**Rationale for Exclusion Criteria**

- |                            |                                                                                                                  |
|----------------------------|------------------------------------------------------------------------------------------------------------------|
| 1, 6, 8, 9,
11, 14 – 19 | In order to ensure safety of the subjects throughout the study                                                   |
| 2, 5, 10,12,
13         | In order to avoid bias for the evaluation of efficacy and safety, including concomitant use of other medications |
| 3, 4, 7                    | To exclude subjects with hepatitis B and liver diseases other than HCV                                           |

**5.2.3 Prior and Concomitant Therapy**

Any medication or vaccine (including over-the-counter or prescription medicines, vitamins and/or traditional Chinese medicine and/or herbal supplements) that the subject is receiving from the time of signing the consent through the DB and OL Treatment Periods and 30 days after study drugs are stopped, must be recorded in the electronic case report form (eCRF) along with the reason for use, date(s) of administration including start and end dates, and dosage information including dose, route and frequency. The investigator should review all concomitant medications for any potential interactions.

Information regarding each subject's qualifying, stable HIV-1 ART medications (allowed regimens will be based on AbbVie approval) including start date, dose and frequency will be recorded into the eCRF at screening. In addition, subjects will be requested to record information for the last two doses of their HIV-1 ART medications taken (dosing date, times, and number of pills) prior to the study visits detailed in [Appendix C](#), and site personnel will record this information in the eCRF.

During the Post-Treatment Period, all medications taken will be recorded until 30 days following the last dose of study drugs. Only medications taken for SAEs and for treatment of HCV and HIV will be recorded thereafter.

The AbbVie Primary Therapeutic Area Medical Director (TA MD) should be contacted if there are any questions regarding concomitant or prior therapies.

### **5.2.3.1 Prior HCV Therapy**

Subjects will be considered treatment-experienced if they have failed prior HCV treatment with IFN [alpha, beta or pegIFN] with or without RBV OR sofosbuvir with RBV with or without IFN. Previous HCV-treatment must have been completed  $\geq 8$  weeks prior to the Screening Visit.

Subjects will be categorized as follows:

- **Treatment-naïve:** subject never received any treatment for HCV infection.
- Subjects with **an allowed prior treatment** will be categorized as follows:
- **Non-responder:** HCV RNA detected at the end of a prior treatment course (except for breakthrough, which is captured separately). These subjects are further categorized as:
  - *Null responder:* failed to achieve a 1 log10 IU/mL reduction in HCV RNA by Week 4 or a 2 log10 IU/mL reduction in HCV RNA by Week 12 during a prior treatment course;

- *Partial responder*: achieved at least a 2 log10 IU/mL reduction in HCV RNA by Week 12 during a prior treatment course but failed to achieve HCV RNA undetectable at the end of treatment;
- *Unknown or Unable to Specify*: insufficient data to categorize as null or partial responder.
- **Breakthrough**: confirmed  $\geq 1$  log10 IU/mL increase from nadir or achieved HCV RNA undetectable (or unquantifiable) during a prior treatment course but HCV RNA was quantifiable during or at the end of treatment.
- **Relapse**: achieved HCV RNA undetectable at the end of a prior treatment course but HCV RNA was detectable following cessation of therapy.
- **Other**: subject received a prior treatment course and reason for not achieving SVR is other than above.
- **Unknown**: subject received a prior treatment course and reason for not achieving SVR is unknown.

Subjects must have discontinued prior HCV therapy at least 8 weeks prior to the Screening Visit in order to be eligible for the study.

### **5.2.3.2 Prior and Concomitant HIV-1 Therapy**

Subjects with HCV/HIV co-infection who are not naïve to HIV ARTs must be on a stable, qualifying HIV-1 ART regimen (allowed regimens will be based on AbbVie approval) for at least 8 weeks prior to screening.

Information regarding each subject's qualifying, stable HIV-1 ART medications including start date, dose and frequency will be recorded into the eCRF at screening. In addition, subjects will be requested to record information for the last two doses of their HIV-1 ART medications taken (dosing date, times, and number of pills) prior to the study visits during the DB and OL Treatment Periods and the Post-Treatment Period detailed in [Appendix C](#), and site personnel will record this information in the eCRF.

Study participants should plan to remain on the same HIV-1 ART regimen for the entire study (both the DB and OL Treatment Periods and Post-Treatment Period). Any change

in the HIV-1 ART regimen during the DB or OL Treatment Period must be discussed with the AbbVie TA MD prior to the change being made, unless the change is being made to address an immediate safety concern.

### **5.2.3.3 Concomitant Therapy**

Subjects should be on stable doses of concomitant medications for at least 2 weeks prior to the initiation of study drugs (8 weeks prior to screening for HIV ARTs). The investigator should confirm that a concomitant medication/supplement can be safely administered with study drugs. Some concomitant medications may require dose adjustments due to the potential for drug-drug interactions. The investigator can also review the label(s) for the concomitant medication(s) for additional information.

The use of hepatoprotective medication (e.g., Sho-saiko-to, Milk thistle, ursodeoxycholic acid, glycyrrhizin acid, SAMe, etc.) is allowed, provided that the drug does not meet any other exclusion criterion.

A subject on a stable dose of a hepatoprotectant should have been on the same dose for at least 2 weeks prior to study entry which begins when the subject signs the informed consent. In addition, the subject should maintain the hepatoprotectant at the same dose throughout the whole study until the end of the Post-Treatment Period. If any change to hepatoprotectant dosing is needed, the investigator should contact the AbbVie TA MD to discuss prior to taking action.

During the Post-Treatment Period, investigators should reassess concomitant medications/supplements, and subjects may resume previously prohibited medications/supplements or revert to pre-study doses after 30 days following discontinuation of active study drugs, as applicable.

### **5.2.3.4 Prohibited Therapy**

Subjects must be able to safely discontinue any prohibited medications or supplements listed in [Table 1](#) at least 2 weeks or 10 half-lives (whichever is longer) prior to the

---

first dose of any study drug and not use these during the entire DB or OL Treatment Periods and for 30 days following discontinuation of active study drugs.

**Table 1. Prohibited Medications and Supplements**

---

Medication or Supplement Name
Red yeast rice (monacolin K), St. John's Wort
Carbamazepine, phenytoin, pentobarbital, phenobarbital, primidone, rifabutin, rifampin
Atorvastatin, lovastatin, simvastatin*
Astemizole, cisapride, terfenadine
Efavirenz containing regimens

---

\* Some HMG-CoA reductase inhibitors (including atorvastatin, lovastatin, or simvastatin) should not be taken with the study drugs. Subjects receiving these statins should either switch to pravastatin or rosuvastatin prior to the first dose of study drugs or may interrupt statin therapy throughout the treatment period and until 30 days after the last dose of study drug, based on the investigator's judgment. If switching to or continuing pravastatin or rosuvastatin, it is recommended to reduce the pravastatin dose by 50% or limit the rosuvastatin dose to 10 mg QD when taking with the study drugs.

Use of ethinyl estradiol containing oral contraceptives with ABT-493 and ABT-530 combination was associated with ALT increases in some healthy female subjects. Hormonal contraceptives (including oral, topical [including vaginal rings], injectable, or implantable varieties) containing ethinyl estradiol may not be used from 2 weeks prior to the first dose of ABT-493/ABT-530 until 30 days after the end of ABT-493/ABT-530 dosing. Progestin-only contraceptives, such as those containing norethindrone, desogestrel, or levonorgestrel, without ethinyl estradiol, may be used with ABT-493/ABT-530. Post-menopausal hormone replacement therapy, such as with esterified or conjugated estrogens, i.e., not containing ethinyl estradiol, may be used with ABT-493/ABT-530 at the discretion of the Investigator.

Anti-HCV medications other than those specified in the protocol will not be allowed anytime during any of the Treatment Periods.

The chronic use of systemic immuno-suppressants is prohibited from 2 weeks prior to the first dose of study drug and until 30 days after the last dose of study drug including, but

not limited to, corticosteroids (prednisone equivalent of > 10 mg/day for > 2 weeks), azathioprine, or monoclonal antibodies (e.g., infliximab).

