**Diagnosis and Main Criteria for Inclusion/Exclusion:**

**Main Inclusion:**

1. Male or female of Asian descent and at least 18 years of age at time of Screening.
2. If female, subject must be either (as defined in section 5.2.4 of the protocol) postmenopausal, OR permanently surgically sterile OR for Women of Childbearing Potential practicing at least one protocol specified method of birth control, starting at Study Day 1 (or earlier) through at least 30 days after the last dose of study drug.
3. Females of childbearing potential must have a negative serum pregnancy test result at Screening, and a negative urine pregnancy test at Study Day 1.  
Females of non-childbearing potential (either postmenopausal or permanently surgically sterile as defined in the protocol) at Screening do not require pregnancy testing.
4. Screening laboratory result indicating HCV GT1, 2, 3, 4, 5 or 6-infection.
5. Subject has positive HCV antibody (Ab) and plasma HCV RNA viral load  $\geq 1000$  IU/mL at Screening Visit.
6. Chronic HCV infection defined as one of the following:
  - Positive for HCV Ab or HCV RNA at least 6 months before Screening;
  - A liver biopsy consistent with chronic HCV infection.
7. Subject must be HCV treatment-naïve (i.e., subject has not received any approved or investigational HCV treatment) or treatment-experienced (i.e., subject has failed prior HCV treatment with IFN [alpha, beta or pegIFN] with or without RBV OR sofosbuvir with RBV with or without IFN). Previous HCV treatment must have been completed  $\geq 8$  weeks prior to screening.

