#### **5.2.1 Inclusion Criteria**

1. Male or female of Asian descent and at least 18 years of age at time of Screening.

2. If female, subject must be either (as defined in section 5.2.4) postmenopausal, OR permanently surgically sterile OR for Women of Childbearing Potential (WOCBP) practicing at least one protocol specified method of birth control starting at Study Day 1 (or earlier) through at least 30 days after the last dose of study drug.

No male contraception is required if the male subject has a female partner who is postmenopausal or permanently sterile (bilateral oophorectomy, bilateral salpingectomy or hysterectomy).

3. Females of childbearing potential must have a negative serum pregnancy test result at Screening, and a negative urine pregnancy test at Study Day 1.

Females of non-childbearing potential (either postmenopausal or permanently surgically sterile as defined in the protocol) at Screening do not require pregnancy testing.

4. Screening laboratory result indicating HCV GT1, 2, 3, 4, 5 or 6-infection.

5. Subject has positive HCV antibody (Ab) and plasma HCV RNA viral load  $\geq 1000$  IU/mL at Screening Visit.

6. Chronic HCV infection defined as one of the following:

- Positive for HCV Ab or HCV RNA at least 6 months before Screening;
- A liver biopsy consistent with chronic HCV infection.

7. Subject must be HCV treatment-naïve (i.e., subject has not received any approved or investigational HCV treatment) or treatment-experienced (i.e., subject has failed prior HCV treatment with IFN [alpha, beta or pegIFN] with or without RBV OR sofosbuvir with RBV with or without IFN). Previous HCV treatment must have been completed  $\geq 8$  weeks prior to screening.

8. Body Mass Index (BMI) is  $\geq 18.0$  kg/m^2 at the time of Screening. BMI is calculated as weight measured in kilograms (kg) divided by the square of height measured in meters (m).

9. Subject must be documented as non-cirrhotic, defined as meeting one of the following criteria:
  - A liver biopsy within 24 months prior to or during screening demonstrating the absence of cirrhosis, e.g., a METAVIR, Batts-Ludwig, Knodell, IASL, Scheuer, or Laennec fibrosis score of  $\leq 3$ , Ishak fibrosis score of  $\leq 4$ ; or
  - A FibroScan® score of  $< 12.5$  kPa within 6 months of Screening or during the Screening Period; or
    - Subjects with indeterminate FibroScan® score ( $12.5 \leq \text{score} < 14.6$ ), must have a qualifying liver biopsy.

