#### **5.2.4 Contraception Recommendations**

If female, subject must be either –

- Postmenopausal defined as:
  - Age  $\geq$  55 years with no menses for 12 or more months without an alternative medical cause.
  - Age < 55 years with no menses for 12 or more months without an alternative medical cause AND an FSH level > 40 IU/L.OR
- Permanently surgically sterile (bilateral oophorectomy, bilateral salpingectomy or hysterectomy).  
OR
- Women of Childbearing Potential (WOCBP):
  - Practicing at least one of the following methods of birth control, on Study Day 1 (or earlier) through at least 30 days after the last dose of study drug–
    - Progestogen-only hormonal contraception (oral, injectable, implantable) associated with inhibition of ovulation, initiated at least 1 month prior to Study Day 1.
    - Bilateral tubal occlusion/ligation.
    - Vasectomized partner(s), provided the vasectomized partner has received medical assessment of the surgical success and is the sole sexual partner of the WOCBP trial participant.
    - Intrauterine device (IUD).

- Intrauterine hormone-releasing system (IUS), excluding ethinyl estadiol.
- Male or female condom with or without spermicide.
- Cap, diaphragm or sponge with spermicide.
- A combination of male condom with either cap, diaphragm or sponge with spermicide (double barrier method).
- True abstinence: Refraining from heterosexual intercourse when this is in line with the preferred and usual lifestyle of the subject (periodic abstinence [e.g., calendar, ovulation, symptothermal, post-ovulation methods] and withdrawal are not acceptable).

If required per local practices, male or female condom with or without spermicide OR cap, diaphragm or sponge with spermicide should be used in addition to one of the birth control methods listed above (excluding true abstinence).

If the male subject has a female partner who is postmenopausal or permanently sterile (bilateral oophorectomy, bilateral salpingectomy or hysterectomy), no contraception is required.

If the male subject is sexually active with female partner(s) of childbearing potential, he must agree from Study Day 1 through 90 days after the last dose of study drug to practice contraception with:

- Condom use and female partner(s) using at least one of the contraceptive measures (as defined in the protocol for female study subjects of childbearing potential).

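### Ethinyl-estradiol contraceptives must stop 2 weeks before first dosing, but a replacement method is required only from Study Day 1, which permits 14 days without contraception

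*Protocol*

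**What the plan says.** Three timing rules bear on this point.

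- **Stop rule.** Section 5.2.3.4, after Table 1: hormonal contraceptives "containing ethinyl estradiol may not be used from 2 weeks prior to the first dose of ABT-493/ABT-530 until 30 days after the end" of dosing. The reason given there is that ALT rose in some healthy women who took such oral contraceptives with the study drugs.
- **Start rule.** Section 5.2.4, for women of childbearing potential: "Practicing at least one of the following methods of birth control, on Study Day 1 (or earlier) through at least 30 days", counted from the final dose. Inclusion criterion 2, in Section 5.2.1 and in the synopsis, sets the same start.
- **Lead-in.** In Section 5.2.4 progestogen-only hormonal methods must be "initiated at least 1 month prior to Study Day 1". No other listed method has such a condition; one example is "Male or female condom with or without spermicide".

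The protocol also requires a negative serum pregnancy test at Screening and "a negative urine pregnancy test at Study Day 1" (criterion 3). Exclusion criterion 1 bars women who are pregnant or considering pregnancy. The rationale table in Section 5.2.1 justifies criteria 2 and 3 by the unknown effect of the two drugs on pregnancy.

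**The concern.** The stop rule and the start rule are two weeks apart, and nothing in the visible text joins them. The protocol withdraws a working contraceptive before dosing and does not say that another must take its place on that day. Women who use no method before Day 1 are uncovered too, but the protocol did not put them in that position.

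The route is a realistic one. Section 5.1.1 allows up to 35 days from Screening to enrolment. A woman who first hears of the stop at Screening and enrols less than a month later cannot meet the progestogen-only lead-in. Unless she already has another qualifying method, she must choose one with no lead-in, and those are the methods with which the gap can arise.

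What is at stake is a conception shortly before exposure to drugs whose effect on pregnancy is unknown. No efficacy or safety analysis depends on it.

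**Working it through.** The plan gives no figure for this gap, so the check is date arithmetic on its own rules.

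**Inputs**
- Latest stop of ethinyl estradiol: 2 weeks before first dosing (Section 5.2.3.4, after Table 1). These contraceptives are not listed in Table 1 itself, so the alternative of 10 half-lives for Table 1 products does not lengthen the period.
- Latest start of a listed method: Study Day 1 (Sections 5.2.1 and 5.2.4).
- Study Day 1: first day of active drug or placebo (Definition of Terms). There is no Day 0 (SAP Section 6.1.2).
- Double-blind urine pregnancy tests: Day 1, then Week 4, then Week 8 or end of treatment (Appendix C).
- Planned arm sizes: 336 in Arm A and 168 in Arm B, 504 in all (Section 8.2, Table 9).

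**Length of the gap**
- Stop period: 2 × 7 = 14 days, Day −14 to Day −1.
- Change to condom, cap/diaphragm/sponge, IUD or IUS on Day 1: 14 days uncovered.
- Change to progestogen-only: start at least 1 month (28 to 31 days) before Day 1. The overlap with ethinyl estradiol used up to the limit is 28 − 14 = 14 to 31 − 14 = 17 days, so the gap is 0.
- With a listed method required from the day of stopping: gap 0.

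**Which arm.** Read literally, the stop counts back from the first dose of ABT-493/ABT-530. For Arm B that is open-label Day 1, when a listed method is already required, so there is no gap. But sites and subjects are blinded (Section 5.5.5), so in practice the stop has to precede Study Day 1 for every woman. Table 1 products are tied instead to the "first dose of any study drug and not use these during the entire DB or OL Treatment Periods", an anchor that works in both arms.

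**Exposure if a conception in the gap were not detected on Day 1.** The next scheduled test is at Week 4, so up to 4 × 7 = 28 days of dosing on the nominal schedule. That is active drug in Arm A only (336/504 = 66.7%). Arm B takes placebo and is tested at Week 4 and again at Week 8 or end of treatment before any active drug. The documents give no detection window for the urine test, so nothing is claimed about what it would miss.

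**How many women.** The documents give no share of women, of childbearing potential or of ethinyl-estradiol use. Assume 30–70% women, 20–40% of them of childbearing potential, and 2–10% of those on ethinyl estradiol:
- Low: 336 × 0.3 × 0.2 × 0.02 = 0.40
- High: 336 × 0.7 × 0.4 × 0.10 = 9.41

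These are Arm A women who would face the stop. Those left uncovered are a subset: progestogen-only users and women who start another method when they stop are not affected.

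**The case against.** The strongest reply is that the rules do not contradict each other. A listed method may start before Day 1, so a woman can change on the day she stops and comply fully. Day 1 is also a defensible anchor, because no study drug is taken before it, and the protocol asks no other woman for pre-dose cover apart from the progestogen-only lead-in. On this view the change would hold former ethinyl-estradiol users to a stricter rule than everyone else. Two negative pregnancy tests and Exclusion criterion 1 stand between the gap and any exposure. Sections 5.4.1 and 6.1.6 provide for a pregnancy on study. The consent pages, which might tell women to change at once, were removed before review.

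Much of this stands. The gap is permitted, not imposed; on a literal reading it does not reach Arm B; harm requires a conception that the Day 1 test misses; the head count rests on assumptions alone; and the consent text cannot be judged. None of it closes the gap, however. Neither the tests nor the exclusion criterion requires contraception. The stricter rule for former users is reasonable, because for them it is the protocol that removes the method.

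**Conclusion.** The concern holds as a minor patient-safety wording point. The protocol as written allows a woman who moves to a method without a lead-in to be uncovered for the 14 days of the stop it mandates, while complying with every stated rule. That conclusion rests only on the protocol's own dates and, for subjects who turn out to be in Arm B, on blinded sites applying the stop before Study Day 1.

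The practical consequence is small and cannot be sized from the documents. The range of 0.4 to 9.4 Arm A women facing the stop holds only under the assumed shares, and the number left uncovered is lower and may be zero. SVR12, blinding and the statistical analysis are unaffected.

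**What to change.** In inclusion criterion 2 (Section 5.2.1), its copy in the synopsis, and Section 5.2.4, add one sentence: a woman of childbearing potential who stops an ethinyl-estradiol contraceptive for the study uses a listed method without ethinyl estradiol from the day she stops. The choice of method stays with her and the investigator.

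As optional tidying, count the ethinyl-estradiol stop back from Study Day 1 in both arms, in line with the rule for Table 1 products.

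The cost is one sentence in three places, with no added visit, test or procedure.

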### **For HCV/HIV-1 Co-Infected Subjects**

The investigator must refer to the current package insert(s) or product label(s) of the subject's ART regimen for a complete list of prohibited medications.

#### **5.2.4 Contraception Recommendations**

If female, subject must be either –

- Postmenopausal defined as:
  - Age  $\geq$  55 years with no menses for 12 or more months without an alternative medical cause.
  - Age < 55 years with no menses for 12 or more months without an alternative medical cause AND an FSH level > 40 IU/L.OR
- Permanently surgically sterile (bilateral oophorectomy, bilateral salpingectomy or hysterectomy).  
OR
- Women of Childbearing Potential (WOCBP):
  - Practicing at least one of the following methods of birth control, on Study Day 1 (or earlier) through at least 30 days after the last dose of study drug–
    - Progestogen-only hormonal contraception (oral, injectable, implantable) associated with inhibition of ovulation, initiated at least 1 month prior to Study Day 1.
    - Bilateral tubal occlusion/ligation.
    - Vasectomized partner(s), provided the vasectomized partner has received medical assessment of the surgical success and is the sole sexual partner of the WOCBP trial participant.
    - Intrauterine device (IUD).

- Intrauterine hormone-releasing system (IUS), excluding ethinyl estadiol.
- Male or female condom with or without spermicide.
- Cap, diaphragm or sponge with spermicide.
- A combination of male condom with either cap, diaphragm or sponge with spermicide (double barrier method).
- True abstinence: Refraining from heterosexual intercourse when this is in line with the preferred and usual lifestyle of the subject (periodic abstinence [e.g., calendar, ovulation, symptothermal, post-ovulation methods] and withdrawal are not acceptable).

If required per local practices, male or female condom with or without spermicide OR cap, diaphragm or sponge with spermicide should be used in addition to one of the birth control methods listed above (excluding true abstinence).

If the male subject has a female partner who is postmenopausal or permanently sterile (bilateral oophorectomy, bilateral salpingectomy or hysterectomy), no contraception is required.

If the male subject is sexually active with female partner(s) of childbearing potential, he must agree from Study Day 1 through 90 days after the last dose of study drug to practice contraception with:

- Condom use and female partner(s) using at least one of the contraceptive measures (as defined in the protocol for female study subjects of childbearing potential).
- True abstinence: Refraining from heterosexual intercourse-when this is in line with the preferred and usual lifestyle of the subject. (Note: Periodic abstinence [e.g., calendar, ovulation, symptothermal, post-ovulation methods] and withdrawal are not acceptable).
- Additionally, male subject agrees not to donate sperm from Study Day 1 through 90 days after the last dose of study drug.

